10.3. Determination of sample size

The target sample size is 832 subjects evaluable for immunogenicity analyses at Visit 4 (416 subjects in each group). Assuming that approximately 35% of enrolled subjects might withdraw or not be evaluable for analyses of immunogenicity, the target sample size to be enrolled is 1280 subjects (640 subjects in each group).

The primary objective of this study is to demonstrate the immune response elicited to all antigens contained in each of the routine infant vaccines *Pediarix*, *Hiberix* and *Prevenar 13* when co-administered with PCV-free liquid HRV vaccine is non-inferior to that elicited when co-administered with the lyophilized HRV vaccine.

10.3.1. Control on type I error

A 2.5% nominal type I error will be used for each co-primary evaluation. To control the type I error below 2.5%, a hierarchical procedure will be used for the multiple study objectives. That is, an objective will be reached if its associated criterion is met and the previous objectives were reached. The same order in which the study objectives are listed in Section 2.1 will be considered for hypothesis testing.

The sample size has been estimated in order to obtain at least 90% power to demonstrate the co-primary objectives. The power associated with the target sample size for the conclusion on each inferential objective of this study is detailed in Section 10.3.3.

10.3.2. Reference for sample size:

References were chosen based on observed response and standard deviations in studies Rota-060 (107531) and Hib-097 (112957).

The percentage of subjects above the cut-off is detailed in Table 16.

Table 16 Percentage of subjects above the cut-off

Study	Timing	Cut-off	N	n	%	LL	UL
Rota-060 (Co-administered group)	Post dose 3	D \geq 0.1 IU/mL	178	178	100	97.9	100
		T \geq 0.1 IU/mL	178	178	100	97.9	100
		HBs \geq 10 mIU/mL [#]	169	169	100	97.8	100
		IPV1 \geq 1:8	128	128	100	97.2	100
		IPV2 \geq 1:8	139	139	100	97.4	100
		IPV3 \geq 1:8	146	146	100	97.5	100
		PRP \geq 0.15 μ g/mL	180	177	98.3	95.2	99.7
		PRP \geq 1 μ g/mL	180	161	89.4	84.0	93.5
Hib-097 (ActHib group)	Post dose 3	D \geq 0.1 IU/mL	273	273	100	98.7	100
		T \geq 0.1 IU/mL	274	274	100	98.7	100
		HBs \geq 10 mIU/mL [#]	258	257	99.6	97.9	100
		IPV1 \geq 1:8	181	181	100	98.0	100
		IPV2 \geq 1:8	192	188	97.9	94.8	99.5
		IPV3 \geq 1:8	323	323	100	98.9	100
		PRP \geq 0.15 μ g/mL	1590	1536	96.6	95.6	97.4
		PRP \geq 1 μ g/mL	274	246	89.8	85.6	93.1
Hib-097 (Pooled Hiberix group)	Post dose 3	D \geq 0.1 IU/mL	393	393	100	99.1	100
		T \geq 0.1 IU/mL	393	393	100	99.1	100
		HBs \geq 10 mIU/mL [#]	363	362	99.7	98.5	100
		IPV1 \geq 1:8	248	246	99.2	97.1	99.9
		IPV2 \geq 1:8	280	275	98.2	95.9	99.4
		IPV3 \geq 1:8	257	254	98.8	96.6	99.8
		PRP \geq 0.15 μ g/mL	1590	1536	96.6	95.6	97.4
		PRP \geq 1 μ g/mL	1590	1291	81.2	79.2	83.1

N= Number of subjects with available results, n (%) = Number (percentage) of subjects with titer/concentration within the specified range, D = Diphtheria, T = Tetanus; IPV1 = Polio virus type 1; IPV2 = Polio virus type 2; IPV3 = Polio

virus type 3; PRP = Polyribosyl-Ribitol-Phosphate; HBs = Hepatitis B; LL/UL = 95% exact CI; #irrespective of whether it was given at birth or not.

The standard deviation for \log_{10} transformed concentrations post-vaccination is presented in [Table 17](#).

Table 17 Standard deviation for \log_{10} transformed titer/concentration post-vaccination

Antigen	Rota-060 Post dose 3 (Co-administration group)	Hib-097 (ActHib group)	Hib-097 (Pooled Hiberix group)
PT	0.257	0.281	0.297
PRN	0.397	0.407	0.409
FHA	0.264	0.255	0.293
Anti-4	0.335	0.295	0.301
Anti-6B	0.549	0.524	0.496
Anti-9V	0.351	0.357	0.381
Anti-14	0.345	0.409	0.405
Anti-18C	0.376	0.336	0.375
Anti-19F	0.332	0.293	0.317
Anti-23F	0.444	0.426	0.447
Anti-1	-	0.337	0.354
Anti-19A	-	0.398	0.358
Anti-3	-	0.281	0.341
Anti-5	-	0.361	0.387
Anti-6A	-	0.350	0.347
Anti-7F	-	0.311	0.326

PT = Pertussis Toxoid, PRN = Pertactin, FHA = Filamentous Hemagglutinin

10.3.3. Power computation

The sample size has been estimated in order to obtain at least 90% power to demonstrate the primary objectives (Bonferroni adjustment of type II error). A hierarchical procedure will be used for the multiple study objectives. That is, an objective will be reached if its associated criterion is met and the previous objectives were reached. The same order in which the study objectives are listed in [Section 2.1](#) will be considered for hypothesis testing.

The power computations were based on the following methods:

- Non-inferiority on percentage of subjects with titer/concentration above pre-specified cut-off: Type II error is obtained using PASS 2005, one-sided non-inferiority test for two proportions, under the alternative of equal proportions (Miettinen and Nurminen method).
- Non-inferiority on GMC: Type II error is obtained using PASS 2005, one-sided non-inferiority test for two from normal data with common variance, under the alternative of equal means;

To account for the multiplicity of comparison, the global type II errors were conservatively estimated as the sum of individual type II errors.

The power associated to the target sample size for the conclusion on each inferential objective of this study is detailed below.

Table 18 details the power for non-inferiority post-dose 3.

Table 18 Power for non-inferiority post-dose 3

	Margin	Reference	N HRV Liq Group	N HRV Lyo Group	Type II error
Anti-D ≥ 0.1 IU/mL	10.0%	99.5%	416	416	0.0%
Anti-T ≥ 0.1 IU/mL	10.0%	99.5%	416	416	0.0%
Anti-IPV1 $\geq 1:8$	5.0%	99.5%	416	416	0.0%
Anti-IPV2 $\geq 1:8$	5.0%	98.8%	416	416	0.1%
Anti-IPV3 $\geq 1:8$	5.0%	99.5%	416	416	0.0%
Anti-HBs ≥ 10 mIU/mL	10.0%	98.0%	416	416	0.0%
Anti-PT GMC	0.67	0.297	416	416	0.0%
Anti-FHA GMC	0.67	0.293	416	416	0.0%
Anti-PRN GMC	0.67	0.409	416	416	0.0%
Anti-1 GMC	0.5	0.549	416	416	0.0%
Anti-3 GMC	0.5	0.549	416	416	0.0%
Anti-4 GMC	0.5	0.335	416	416	0.0%
Anti-5 GMC	0.5	0.549	416	416	0.0%
Anti-6A GMC	0.5	0.549	416	416	0.0%
Anti-6B GMC	0.5	0.549	416	416	0.0%
Anti-7F GMC	0.5	0.549	416	416	0.0%
Anti-9V GMC	0.5	0.381	416	416	0.0%
Anti-14 GMC	0.5	0.409	416	416	0.0%
Anti-18C GMC	0.5	0.376	416	416	0.0%
Anti-19A GMC	0.5	0.549	416	416	0.0%
Anti-19F GMC	0.5	0.332	416	416	0.0%
Anti-23F GMC	0.5	0.447	416	416	0.0%
Anti-PRP ≥ 0.15 μ g/mL	5.0%	96.5%	416	416	4.8%
Anti-PRP ≥ 1 μ g/mL	10.0%	81.2%	416	416	4.4%
Seroresponse to PT\$	10.0%	0.297	416	416	0.1%
Seroresponse to FHA\$	10.0%	0.293	416	416	0.1%
Seroresponse to PRN\$	10.0%	0.409	416	416	0.1%
Global Power > 90.0%					

N = Number of evaluable subjects per group, Anti-D = anti-diphtheria antibody, Anti-T = anti-tetanus antibody, Anti-IPV1 = anti-poliovirus type 1, Anti-IPV2 = anti-poliovirus type 2, Anti-IPV3 = anti-poliovirus type 3, Anti-PT = anti-pertussis toxoid antibody, Anti-FHA = anti-filamentous hemagglutinin, Anti-PRN = anti-pertactin antibody, Anti-PRP = antibodies against polyribosyl-ribitol-phosphate; Anti-HBs = antibodies against hepatitis B.

For Anti-PRP, anti-D, anti-T, anti-IPV1, anti-IPV2 and anti-IPV3 antibodies, the reference used for power calculation is rate. For the rest of the antibodies, the standard deviation values were considered.

*For rates ~100%, a conservative reference of 99.5% is taken.

\$Power results were based on the simulation assuming the distribution of immune response from *HRV Liq group* and *HRV Lyo group* are the same, and equal sero-response rate between groups under the alternative (seroresponse for

anti-PT, anti-FHA and anti-PRN in *HRV liq* group were defined as the percentage of subjects showing an antibody concentration above a threshold that led to 95% seroresponse in the *HRV lyo*), 1-sided, alpha=0.025.

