10.4.2. Per-protocol Set for analysis of immunogenicity

The PPS for immunogenicity will include all eligible subjects from the ES:

- who have received the study vaccines according to their random assignment,
- who comply with the vaccination schedule of routine infant vaccines and HRV vaccines as per [Table 19](#),
- for whom the routine infant vaccines were administered according to the protocol as per [Table 10](#),
- for whom the HRV vaccine liquid or lyophilized formulation was administered according to protocol,
- who have not received a vaccine not specified or forbidden in the protocol up to Visit 4 blood sampling,
- who had not received medication forbidden by the protocol up to Visit 4 blood sampling,
- whose underlying medical condition(s) was (were) not forbidden by the protocol up to Visit 4 blood sample,
- for whom data concerning immunogenicity endpoint measures are available. This will include subjects for whom assay results are available for antibodies against at least one routine infant vaccine antigen component,
- who comply with the blood sampling schedule after the 3rd dose of Pediarix, Hiberix and Prevenar 13 as per [Table 19](#),
- who have no concomitant infection up to Visit 4 blood sample, which may influence the immune system.

Table 19 Maximum allowed interval between visits

Interval	Allowed length of interval
Visit 1 → Visit 2	49 days-83 days after Dose 1 of study vaccines 1
Visit 2 → Visit 3	56 days-83 days after Dose 2 of study vaccines 1
Visit 3 → Visit 4	21 days-48 days after Dose 3 of study vaccines 1
Visit 3 → ESFU	180 days-210 days after Dose 3 of study vaccines

¹ Subjects will not be eligible for inclusion in the Per-Protocol Set (PPS) for analysis of immunogenicity, if they make the study visit outside this interval. This is not applicable for the interval between Visit 3 and ESFU.

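### Do the polio inputs of Protocol Table 18 put the claim of more than 90% global power in doubt?

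*Protocol*

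**What the plan says.** Section 10.3.2 of the protocol takes its references from two earlier studies, in three groups: Rota-060 co-administration, Hib-097 ActHib and Hib-097 pooled Hiberix. It does not say how a value is chosen or combined across groups. Table 16 gives these rates, in that order of groups:

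- IPV1: 100%, 100%, 99.2%
- IPV2: 100%, 97.9%, 98.2%
- IPV3: 100%, 100%, 98.8%

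Table 18 in section 10.3.3 uses 99.5% for IPV1 and IPV3 (type II error 0.0%) and 98.8% for IPV2 (0.1%). All three have a 5% margin and 416 subjects per group. A footnote says "For rates ~100%, a conservative reference of 99.5% is taken". Another defines the sample size column: "N = Number of evaluable subjects per group". On combining the criteria, "the global type II errors were conservatively estimated as the sum of individual type II errors", and the table ends with "Global Power > 90.0" per cent.

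**The concern.** In the other 24 of the 27 rows, the reference is the least favourable source value or a more cautious one. Anti-HBs is 98.0% against a lowest observed 99.6%, PRP ≥ 0.15 µg/mL is 96.5% against 96.6%, and every standard deviation is at or above the largest in Table 17. Only the three polio rows are more favourable than the worst source group, and for two of them the value is labelled conservative. The IPV2 rate and error also do not agree with each other.

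Table 16 has odd entries in its ActHib block as well:

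- PRP ≥ 0.15 repeats the pooled Hiberix 1536/1590, while PRP ≥ 1 has N = 274.
- IPV3 has N = 323, against 273 for anti-D.
- The IPV2 upper limit is printed as 99.5, but 188/192 gives an exact limit of 99.43.

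Polio has the tight margin and belongs to the first co-primary objective. With 0.4 points of slack, slightly worse polio inputs might turn a claim of more than 90% into one of less.

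**Working it through.** **Method.** One-sided 2.5% Miettinen-Nurminen test with equal true rates p and n = 416 per group, as section 10.3.3 states. For margin δ,

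β = 1 − Φ[(δ − 1.96·s0)/s1], with s1 = √(2p(1−p)/n) and s0 = √([p̃1(1−p̃1) + p̃2(1−p̃2)]/n),

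where p̃1 and p̃2 are the maximum-likelihood rates restricted to p̃2 − p̃1 = δ.

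**Step 1: reproduce the plan.**

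- PRP ≥ 0.15 (p = 96.5%, δ = 5%): s0 = 0.01467, s1 = 0.01274. (0.05 − 1.96 × 0.01467)/0.01274 = 1.668, so β = 4.77% (printed 4.8%).
- PRP ≥ 1 (p = 81.2%, δ = 10%): s0 = 0.02740, s1 = 0.02709. (0.10 − 1.96 × 0.02740)/0.02709 = 1.709, so β = 4.37% (printed 4.4%).
- Seroresponse: 3 × 0.1% = 0.3%, as printed.
- The GMC, D, T and HBs rows are 0.0%.

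Printed sum: 0.1 + 4.8 + 4.4 + 0.3 = 9.6%, so power is 90.4%. Unrounded, with IPV2 at 0.02%: 0.02 + 4.77 + 4.37 + 0.30 = 9.46%, so 90.5%. The claim reproduces.

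**Step 2: polio errors at other rates (δ = 5%).**

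| Rate | Where it occurs | s0 | s1 | β |
|---|---|---|---|---|
| 99.5% | Table 18, IPV1 and IPV3 | 0.01122 | 0.00489 | 0.00% |
| 99.2% | IPV1, pooled Hiberix | 0.01155 | 0.00618 | 0.00% |
| 98.8% | Table 18 IPV2; IPV3, pooled Hiberix | 0.01200 | 0.00755 | 0.02% |
| 98.2% | IPV2, pooled Hiberix | 0.01269 | 0.00922 | 0.32% |
| 97.9% | IPV2, ActHib | 0.01304 | 0.00994 | 0.70% |

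Replacing 99.5% by the lower observed rates costs nothing for IPV1 and 0.02 points for IPV3. For IPV2, the printed 0.1% is larger than the 0.02% that belongs to 98.8%, so the slip is on the safe side.

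**Step 3: where 98.8% may come from.** Rota-060 plus pooled Hiberix gives (139 + 275)/(139 + 280) = 414/419 = 98.8% for IPV2. The same pool gives 374/376 = 99.5% for IPV1 and 400/403 = 99.3% for IPV3. IPV1 and IPV3 follow the printed footnote value in any case. The inputs are plausible, but the rule is not written down.

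**Step 4: the sum under alternative inputs.**

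| Polio rates (IPV1/2/3) | PRP ≥ 0.15 | Sum of errors | Power |
|---|---|---|---|
| 99.2/98.2/98.8 (pooled Hiberix) | 96.5% | 0.00 + 0.32 + 0.02 + 4.77 + 4.37 + 0.30 = 9.78% | 90.2% |
| 99.2/97.9/98.8 (lowest of any group) | 96.5% | 0.00 + 0.70 + 0.02 + 4.77 + 4.37 + 0.30 = 10.16% | 89.8% |
| 99.2/97.9/98.8 | 96.6% (Table 16) | 0.00 + 0.70 + 0.02 + 4.37 + 4.37 + 0.30 = 9.76% | 90.2% |

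With exact rather than asymptotic type II errors, the first two rows become 91.1% and 90.8%. If the criteria were independent and their powers multiplied, the second row would be 90.1%.

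**Step 5: the odd Table 16 cells.** None alters a Table 18 input. The pooled Hiberix block gives the same 96.6% for PRP ≥ 0.15 and a lower IPV3 rate than the ActHib block. The upper limit of an interval is not used in the power calculation.

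**The case for a change.** The strongest counter-argument is consistency. If 24 rows follow the worst source group and polio followed it too, the plan's own sum would give 89.8%, below the stated claim. That figure is correct, but it needs two choices at once: the ActHib rate for IPV2, although every subject in this trial receives Hiberix, and a PRP rate kept 0.1 point below its source. The protocol promises no worst-group rule, and a shortfall of 0.2 points in a deliberately pessimistic sum does not show that 416 per group is too few.

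A second argument is that 416 polio results per group may not be available. Entry to the per-protocol set requires only that "assay results are available for antibodies against at least one routine infant vaccine antigen component", missing results are not replaced, and in the pooled Hiberix block of Table 16 polio N is 248 to 280 against 393 for anti-D. The dependence is real. With pooled Hiberix rates and the other rows as printed (4.77 + 4.37 + 0.30 = 9.44%), the polio errors at 395 results per group are 0.00 + 0.48 + 0.04 = 0.52%, which keeps power at 90.0%. At an assumed 350 they are 0.01 + 1.14 + 0.15 = 1.30%, giving 89.3%. At an assumed 300 they are 0.07 + 2.82 + 0.61 = 3.50%, giving 87.1%. However, the documents give no expected polio availability and no reason for the lower counts in the earlier study. The allowance of 35% non-evaluable subjects (640 × 0.65 = 416) may cover such losses, and polio ranks fourth of ten in assay priority in Table 8. The assumption is also not hidden, since 416 is printed on each polio row.

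What stands is editorial. The choice of polio references is not explained, the word conservative does not fit IPV1 and IPV3 when set against pooled Hiberix, the IPV2 rate and error differ by less than 0.1 point, and three ActHib cells look like copying or rounding slips.

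**Conclusion.** No change to the plan is called for. At 416 polio results per group, the pooled Hiberix rates give a summed-error power of 90.2%, so the claim of more than 90% stands. Across the source choices above, the plan's method gives 89.8% to 90.5%, and exact errors stay above 90% for both sets of polio rates. The IPV1 and IPV3 references matter by 0.02 points or less, and the IPV2 mismatch is in the cautious direction. These are planning figures: they enter no test, margin, analysis set or interpretation rule. Restating them would leave enrolment and every possible trial conclusion as they are. The conclusion rests on the 35% allowance delivering close to 416 polio results per group, which Table 18 states as its N and which the documents give no firm reason to doubt.

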10.4. Sets for Analyses

10.4.1. Exposed Set

- The Exposed Set (ES) will include all subjects with at least one study vaccine administration documented. A safety analysis based on the ES will include all vaccinated subjects.
- An immunogenicity analysis based on the ES will include all vaccinated subjects for whom immunogenicity data is available.

The ES analysis will be performed per treatment actually administered at Dose 1.

10.4.2. Per-protocol Set for analysis of immunogenicity

The PPS for immunogenicity will include all eligible subjects from the ES:

- who have received the study vaccines according to their random assignment,
- who comply with the vaccination schedule of routine infant vaccines and HRV vaccines as per [Table 19](#),
- for whom the routine infant vaccines were administered according to the protocol as per [Table 10](#),
- for whom the HRV vaccine liquid or lyophilized formulation was administered according to protocol,
- who have not received a vaccine not specified or forbidden in the protocol up to Visit 4 blood sampling,
- who had not received medication forbidden by the protocol up to Visit 4 blood sampling,
- whose underlying medical condition(s) was (were) not forbidden by the protocol up to Visit 4 blood sample,
- for whom data concerning immunogenicity endpoint measures are available. This will include subjects for whom assay results are available for antibodies against at least one routine infant vaccine antigen component,
- who comply with the blood sampling schedule after the 3rd dose of Pediarix, Hiberix and Prevenar 13 as per [Table 19](#),
- who have no concomitant infection up to Visit 4 blood sample, which may influence the immune system.

Table 19 Maximum allowed interval between visits

Interval	Allowed length of interval
Visit 1 → Visit 2	49 days-83 days after Dose 1 of study vaccines 1
Visit 2 → Visit 3	56 days-83 days after Dose 2 of study vaccines 1
Visit 3 → Visit 4	21 days-48 days after Dose 3 of study vaccines 1
Visit 3 → ESFU	180 days-210 days after Dose 3 of study vaccines

¹ Subjects will not be eligible for inclusion in the Per-Protocol Set (PPS) for analysis of immunogenicity, if they make the study visit outside this interval. This is not applicable for the interval between Visit 3 and ESFU.

10.5. Derived and transformed data

- A seronegative subject is a subject whose antibody concentration is below the cut-off value.
- A seropositive subject is a subject whose antibody concentration is greater than or equal to the cut-off value. The applicable thresholds are presented in [Table 7](#).
- A seroprotected subject is a subject whose antibody concentration is greater than or equal to the level defining clinical protection. The following seroprotection thresholds are applicable:
 - anti-D antibody concentrations ≥ 0.1 IU/mL.
 - anti-T antibody concentrations ≥ 0.1 IU/mL.
 - anti-HBs antibody concentrations ≥ 10 mIU/mL.
 - anti-poliovirus types 1, 2 and 3 antibody titers ≥ 8 ED50.
 - anti-PRP antibody concentrations ≥ 0.15 μ g/mL.
- Other cut-offs to be considered:
 - anti RV IgA antibody concentration ≥ 90 U/mL.
 - anti-pneumococcal serotypes (1, 3, 4, 5, 6A, 6B, 7F, 9V, 14, 18C, 19A, 19F, 23F) antibody concentrations ≥ 0.35 μ g/mL for the ELISA.
 - anti-PRP antibody concentrations ≥ 1.0 μ g/mL.
- The GMC calculation will be performed by taking the anti-log of the mean of the log concentration transformations. Note that antibody concentrations below the cut-off of the assay will be given an arbitrary value of half the cut-off while antibody concentration above the assay cut-off but below the Limit of Quantification will be given the assay cut-off as value.

Handling of missing data:

Immunogenicity:

- For a given subject and a given immunogenicity measurement, missing or non-evaluable measurements will not be replaced.

Reactogenicity and Safety:

- For analysis of solicited, unsolicited AEs (such as SAEs or AEs by primary MedDRA term), and for the analysis of concomitant medications, all vaccinated subjects will be considered. Subjects who did not report the event or the concomitant medication will be considered as subjects without the event or the concomitant medication respectively.

10.6. Analysis of demographics

The median, mean, range and standard deviation of age (in weeks) at each study vaccine dose and of the gestational age will be computed by group. The median, mean and standard deviation of length (in centimeters) and weight (in kilograms) at Visit 1 will be computed by group. The racial and sex composition of the subjects will be presented.

The distribution of subjects enrolled among the study centers will be tabulated as a whole and per group.

The number of subjects who withdraw from the study will be tabulated by group according to the reason for drop-out.

The deviations from specifications for age and intervals between study visits will be tabulated by group.

10.7. Analysis of immunogenicity

The primary analysis will be based on the PPS for analysis of immunogenicity. An analysis on the ES will be performed only if, in any group, more than 5% of the vaccinated subjects with immunological data are excluded from the PPS for immunogenicity.

The following section describes the analyses that will be performed.

10.7.1. Within group analysis

For each treatment group, one month after Dose 3 of routine infant vaccines at Visit 4 (Month 5) time-point:

- Seroprotection rates against HBsAg, diphtheria toxoid, tetanus toxoid, PRP antigen and poliovirus types 1, 2 and 3 (with exact 95% CI) will be calculated.
- Seropositivity rates and their exact 95% CIs for antibodies against PT, FHA, PRN, anti-rotavirus, S. pneumoniae serotypes 1, 3, 4, 5, 6A, 6B, 7F, 9V, 14, 18C, 19A, 19F, 23F and HBsAg will be tabulated.
- Percentage of subjects with anti-pneumococcal serotypes (1, 3, 4, 5, 6A, 6B, 7F, 9V, 14, 18C, 19A, 19F, 23F) antibody concentrations $\geq 0.35 \mu\text{g/mL}$ with 95% CI will be calculated.

- Percentage of subjects with anti-PRP antibody concentrations $\geq 1.0 \mu\text{g/mL}$ will be calculated with 95% CI.
- Percentage of subjects with anti RV IgA antibody concentration $\geq 90 \text{ U/mL}$ will be calculated with 95% CI.
- GMC/GMT with 95% CI will be tabulated for antibodies against each antigen.

The above mentioned descriptive analyses will also be performed by race and sex.

The distribution of antibody concentrations/titers for each appropriate serotype/antigen will be displayed using tables and/or reverse cumulative distribution curves.

For anti-HBs antibodies, an analysis will be done according to vaccination history to Hepatitis B vaccine.

10.7.2. Between group assessment

For each treatment group, one month after Dose 3 of routine infant vaccines at Visit 4 (Month 5) time-point:

- Two-sided asymptotic standardized 95% CIs for the difference in the percentage of subjects with titer/concentration above or equal to pre-specified clinical thresholds will be computed (HRV Liq group minus HRV Lyo group).
- The two-sided 95% CIs for the group GMC/GMT ratio (HRV Liq group over HRV Lyo group) will be computed using an ANOVA model on the logarithm10 transformation of the concentrations. The ANOVA model will include the vaccine group as fixed effects. In addition, for anti-HBs, the model will include the Hepatitis B vaccination history as co-variable.
- For the group comparison in anti-PT, FHA, PRN seroresponse at one month post dose 3, P-value for testing H0: $P \leq 85\%$ vs. H1: $P > 85\%$ ($P = \text{ % of subjects in HRV liq group with seroresponse (above a threshold that leads to 95\% seroresponse in the HRV lyo group) }$) will be computed. P-value will be computed by integrating on the p-value for the null hypothesis that the seroresponse rate in the HRV lyo group is $< 85\%$ and the a-posteriori probability of the threshold in the HRV liq group.

